11.3 Sample size and analytical methodology

To estimate the sample size for stratum 1 (typical SFT), a 1-stage phase II design has been used, having considered the published response rate based on Choi criteria in SFT patients which correspond to 40% in monotherapy. For a design with $P_0=0.40$, $P_1=0.60$; $\alpha=0.1$ and $\beta=0.2$. Thus, 30 patients should be enrolled into the study, and to reject the null hypothesis for the typical SFT stratum 16 responses or more (Choi criteria), out of the 30 patients, are needed.

To estimate the sample size for stratum 2 (malignant-dedifferentiated SFT), a Simon 2-stage phase II design has been used, having considered the published response rate based on Choi criteria in SFT patients which correspond to 40% in monotherapy. For a design with $P_0=0.40$, $P_1=0.60$; $\alpha=0.1$ and $\beta=0.2$. At the first stage, 23 patients should be enrolled into the study, if there are fewer than 12 responses (11 or less) the trial will be terminated and it will be concluded that pazopanib is not sufficiently active. At the second stage, another 8 patients (total 31 patients) would be enrolled into the study. To reject the null hypothesis for the SFT stratum 16 responses or more (Choi criteria), out of the 31 patients, are needed.

To estimate the sample size for stratum 3 (EMC), a 1-stage phase II design has been used, having considered the published response rate based on RECIST criteria. For a design with $P_0=0.05$, $P_1=0.20$, $\alpha=0.1$ and $\beta=0.2$. Thus, 21 patients should be enrolled into the study, and to reject the null hypothesis for the EMC stratum 3 responses or more (RECIST criteria), out of the 21 patients, are needed.

For variables that follow binomial distributions (i.e. response rate) frequency and percentages will be calculated, together with their correspondent exact 95% confidence intervals. For time-to-event variables (i.e. PFS or OS) Kaplan-Meier estimations will be used. To analyze the reduction of risk and the influence of other variables on time-to-event variables Cox Regression will be applied. To correlate pharmacodynamics markers and biomarkers with clinical response standard methods for bivariate and multivariate regression and correlation will be used. Multivariate methods will be used only if the required assumptions are verified.

11.4 Efficacy analysis

Disease should be captured (with CT or MRI scan) and target/non-target identified at baseline. All the baseline disease assessments should be completed within 28 days prior to the date of inclusion in the trial. Subsequently, imaging studies required to investigate known disease should be done every 8 weeks (until tumor progression is documented in patients with complete response, partial response or stable disease). Patients who have not progressed but discontinued treatment due to toxicity or other reasons unrelated to tumor progression will still be re-evaluated every 8 weeks, unless they have started a new anti-cancer therapy.

Efficacy assessment populations:

- Intent to treat (ITT) analysis: Efficacy analysis will be carried out in the ITT population. All patients participating in the study will be included in the analysis of efficacy.
- Per Protocol (PP) analysis: Efficacy analysis will be carried out in per protocol population. All patients participating in the study and having received at least 3 weeks of treatment with pazopanib with no major protocol deviations will be included in the analysis of efficacy.

11.5 Safety analysis

Any patient included in the study receiving at least a single dose of study medication will be evaluable for the toxicity analysis. Safety profile will be characterized by treatment-emergent Adverse Events (TEAE), vital signs and laboratory abnormalities. Assessment of adverse events will include type, incidence, severity (graded by the National Cancer Institute [NCI] Common Terminology Criteria for Adverse Events [CTCAE], Version 4.0), timing, seriousness, and relatedness; and laboratory abnormalities. Baseline tumor-related signs and symptoms will be recorded as adverse events during the trial if they worsen in severity or increase in frequency. In each study visit all adverse events will be registered according to NCI-CTC version 4.0.

12. TRANSLATIONAL STUDY

12.1 Rationale

SFTs show a well-developed and characteristic pattern of thin-walled branching hemangiopericytoma-like vessels under the microscope. There is a strong clinical benefit of antiangiogenic therapy in relapsed SFT. Nevertheless, the mechanisms regulating neoangiogenesis in SFT have not been described. Pazopanib is a tyrosine kinase inhibitor (TKI) that targets many angiogenic factors, including VEGFR-1, VEGFR-2, VEGFR-3, PDGFR α , PDGFR β and c-KIT. Then, the impact of pazopanib on the angiogenic process in SFT will be investigated. EMC is a very rare soft tissue sarcoma little responsive to standard cytotoxic chemotherapy. There are preliminary data on the activity of sunitinib in this histotype. The mechanism of action of antiangiogenic in this sarcoma is still to be defined.

12.2 Translational objectives

SFT cohorts:

- To perform a central pathologic review (diagnosis confirmation) of paraffin-embedded tumor blocks for each recruited patient with SFT, including (exploratory) STAT6 immunohistochemistry.
- To evaluate the serum profile of serum cytokine markers as indicator of response to pazopanib. The Luminex technology will be employed for the analysis of 12 cytokines [VEGF-A, PIGF-1, SDF-1 alpha (CXCL12), TNF alpha, IL-8, IL-6, PDGF –beta, HGF, E-Selectine, ICAM1, MMP-9 and FGFb].
- To evaluate the profile of angiogenic markers in the primary tumor and/or in the subsequent biopsies. Microvessel density (MVD) and VEGF/PDGF pathways will be evaluated by IHQ expression as well as their correlation with prognosis and their role as predictive factors to treatment with pazopanib (response, PFS and OS).
- To evaluate pharmacodynamic markers (MVD, VEGF/PDGF) only in patients with paired samples (in the biopsies taken after treatment).

EMC cohort:

- To perform a central pathologic review (diagnosis confirmation) of paraffin-embedded tumor blocks for each recruited patient with EMC, including FISH analysis and/or RT-PCR NR4A3 and its partners (EWSR1, TAF15).
- To evaluate the expression and activation profile of angiogenic targets (VEGFR, PDGFR, RET, MCSR1) in the primary tumor and/or in the subsequent biopsies by immunohistochemistry, pRTK array and IP/WB respectively.

12.3 Biological sample collection

The samples to be collected for both SFT and EMC patients are:

1. One representative paraffin-embedded tumor block of the diagnostic biopsy/resection (mandatory) taken at pre-treatment stage (screening).
2. Three 5-mL tubes of peripheral blood within 72 hours prior to starting treatment (baseline).
3. One representative paraffin-embedded tumor block (selected patients for whom post-treatment biopsy could be performed).
4. Three 5-mL tubes of peripheral blood within 72 hours after radiological response is documented.
5. Three 5-mL tubes of peripheral blood at the end of treatment (within 72 hours after progressive disease is documented).

12.4 Translational analytical methods

In the case of serum, the kinetic profile of each biomarker will be considered (increased, constant, decreased). All parameters analyzed will be correlated with progression-free survival (PFS), objective tumor response, overall survival (OS) and histopathological parameters.

For the statistical analysis, binary variables will be used, which will reflect the positivity status of measurements (yes/no; presence; absence).

The association with histopathological parameters and objective tumor response, all categorical, will be calculated through chi-squared test in order to determine the homogeneity or lineal tendency for the ordinary variables.

The statistical significance level will be of 5%. With the aim of studying the impact of histology, immunohistochemistry and molecular factors on PFS and OS, the proportional method Kaplan-Meier (log rank) will be used. The evidence of relative risk for each patient will be provided by means of a Cox proportional hazards model, by using a stepwise selection to identify the independent predictors of poor outcome.

Multivariate analysis will be performed for the biomarker study if the number of cases available for the study is at least 10-fold the number of variables involved. Otherwise, standard univariate pre and post tests will be used.

For the shipment of biological samples, please contact:

Sofpromed Investigación Clínica, SLU
[name], [name]
[name], [name]
[contact]
[contact]
[contact]
E-mail: [contact]

An additional document will be provided in the Investigator Site File with detailed guidelines regarding biological sample management.

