11. STUDY DESIGN AND STATISTICS

11.1 Study design

GEIS-32 is a phase II, open-label, non-randomized, multicenter clinical trial with three strata (1-a typical SFT, 1-b malignant/dedifferentiated SFT and 2 EMC). The study will be developed at international level with 8 sites in Spain, 5 sites in Italy and 5 sites in France, during a recruitment period of 36 months. Patients will receive oral pazopanib at 800 mg once daily continuously. Patients will continue to receive treatment until there is evidence of progressive disease, unacceptable toxicity, non-compliance, withdrawn consent or investigator decision. The IMP will be investigated separately in the cohorts.

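### Section 12.4 fixes the chi-squared test for marker–response associations, and the sparse tables expected in the 21-patient EMC stratum can make its p-value unreliable (minor; translational analyses)

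*Protocol*

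**What the plan says.** Section 12.4 sets out the marker analysis. Markers are dichotomised: "For the statistical analysis, binary variables will be used, which will reflect the positivity status of measurements". The scope is broad: "All parameters analyzed will be correlated with progression-free survival (PFS), objective tumor response, overall survival (OS) and histopathological parameters". The test is named: "The association with histopathological parameters and objective tumor response, all categorical, will be calculated through chi-squared test", with a linear-trend form for ordered variables. The significance level is 5%.

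Neither 12.4 nor 11.3 mentions an exact test for association, a continuity correction or a rule for small expected counts. In 11.3 the word exact is attached only to the binomial confidence intervals.

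Section 12.2 gives the EMC cohort its own marker list: "To evaluate the expression and activation profile of angiogenic targets (VEGFR, PDGFR, RET, MCSR1", and so on. Section 11.1 adds: "The IMP will be investigated separately in the cohorts". Section 11.3 sizes EMC on response rates of 5% (null) and 20% (alternative): "Thus, 21 patients should be enrolled into the study, and to reject the null hypothesis for the EMC stratum 3 responses or more (RECIST criteria").

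**The concern.** The chi-squared test relies on a large-sample approximation that needs reasonable expected counts in every cell. EMC cannot supply them: even if the drug works as hoped, about 4 of 21 patients respond. The reported p-value may then differ from the exact one by a factor of two to five, and significance at 5% can rest on one to three patients. Evaluating markers is a stated objective and section 15.5 plans separate publication of the translational results. In so rare a tumour, a spurious marker signal would be hard to correct later.

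**Working it through.** **Inputs.** EMC n = 21, rates 0.05 and 0.20, success at 3 or more responses (11.3). Binary markers, chi-squared test, 5% level (12.4). SFT strata of 30 and 31 patients, rates 0.40 and 0.60 (Trial Summary and 11.3). Marker prevalence is not in the document and is varied below.

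**The plan's own design reproduces.** With n = 21 and 3 or more responses, the exact binomial gives P(X ≥ 3 | 0.05) = 0.085 and P(X ≥ 3 | 0.20) = 0.821. Both meet the stated limits of 0.1 and 80% power.

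**Expected counts.** Expected responders are 21 × 0.05 = 1.05 and 21 × 0.20 = 4.2. With R responders and K marker-positive patients, the smallest expected count is at most R × 10/21. For R = 4 this is 40/21 = 1.90, so it is below 2 for every R up to 4. The probability of 4 or fewer responders is 0.59 at a 20% response rate and above 0.99 at 5%. Sparse tables are therefore the usual EMC case.

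**Illustrative tables.** Let a and b be marker-positive and marker-negative responders, and c and d the same for non-responders. Uncorrected Pearson: X² = n(ad − bc)² / [R(n − R)K(n − K)]. When every responder is marker-positive, as in these three tables, two-sided Fisher p = C(K,R)/C(21,R), because no other table with the same margins is as improbable.

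| R | K | X² | Chi-squared p | Fisher p |
|---|---|---|---|---|
| 1 | 4 | 21 × 17² / (1×20×4×17) = 4.46 | 0.035 | 4/21 = 0.190 |
| 2 | 7 | 21 × 28² / (2×19×7×14) = 4.42 | 0.0355 | 21/210 = 0.100 |
| 3 | 10 | 21 × 33² / (3×18×10×11) = 3.85 | 0.0497 | 120/1330 = 0.090 |

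The third row sits at the protocol's own EMC success threshold, with a marker positive in about half the patients.

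**Conditional false-positive rate.** Fix R and K, assume no association, and add the hypergeometric probabilities of all tables that uncorrected chi-squared declares significant at 5%. The maximum over K = 2 to 19 is:

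| Responders | Maximum rate | At K = |
|---|---|---|
| 1 | 19.0% | 4 or 17 |
| 2 | 18.6% | 2 or 19 |
| 3 | 9.0% | 10 or 11 |
| 4 | 9.0% | 10 or 11 |
| 5 | 11.1% | 8 or 13 |

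For K = 1 or 20 the rate is 14.3% with 3 responders and 19.0% with 4. With 1 responder and K from 5 to 16, chi-squared is never significant.

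**Averaged over tables.** With R and K both binomial, response 5–20% and marker prevalence 10–50%, n = 21:

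| Test | Size at nominal 5% |
|---|---|
| Chi-squared, uncorrected | 0.9–6.7% |
| Fisher | 0.15–2.0% |
| Fisher mid-p | 0.8–3.9% |

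**SFT.** Expected responders run from 30 × 0.40 = 12 to 31 × 0.60 = 18.6. At n = 30 the average size of chi-squared is about 3–5%. Conditional peaks occur for rare markers: 10.3% with 14 or 16 responders and 4 positive, and 12.8% with 12 or 18 responders and 5 positive.

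**The case against.** - **Average size.** On average chi-squared is not badly inflated, and in many EMC scenarios it is below 5%. This stands. A reader might infer that the test overstates significance throughout, or that the approximation fails in all three strata. The averages above do not support either reading.
- **Selected examples.** The one-responder table needs exactly 1 responder (probability 0.38 at a 5% response rate, 0.05 at 20%) and 4 of 21 marker-positive patients, a prevalence the protocol does not give. It is tempting to conclude that any single EMC responder could produce a significant marker. That happens only when at most 4 patients share that responder's marker status. The examples show what can happen, not what will.
- **Which chi-squared.** With a continuity correction the three p-values become 0.42, 0.19 and 0.18. This is fair, but 12.4 specifies no correction. That an unspecified option moves p from 0.035 to 0.42 is a reason to settle the wording.
- **EMC objective.** Section 12.2 states prediction of response only for the SFT cohorts. EMC comes in through the general sentence of 12.4 that all parameters are correlated with response. The 2x2 layout also assumes responder against non-responder. Both points limit the weight of the finding, but neither removes EMC from the rule as written.
- **Detail for the analysis plan.** A sparse-cell rule could sit there, and its absence alone would be no finding. Here the protocol itself names the test, so an analysis plan that follows it to the letter inherits the problem.

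**Conclusion.** The point holds as a minor one, mainly for EMC. Applied as written, 12.4 can return a p-value two to five times too small in individual EMC tables, with conditional error up to 19% for 1 or 2 responders and 9–11% for 3 to 5 (2 to 19 marker-positive patients). This assumes the uncorrected statistic, a responder/non-responder split, and marker prevalences that the protocol does not state. The document does not support a claim of uniform inflation: average size is 0.9–6.7% at n = 21. Nor does it support extending the low responder counts to SFT, where 12 to about 19 responders are expected and only rare or nearly universal markers are materially affected. The primary endpoint and its decision rules do not depend on this test.

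**What to change.** In 12.4, state that when any expected cell count is below 5, Fisher's exact test replaces the chi-squared test, and an exact permutation trend test replaces the chi-squared trend test for ordered categories. Keep chi-squared otherwise.

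The change is wording only: no patients, visits or samples are added. The statistical cost should be acknowledged. At n = 21 Fisher's test has an average size of about 0.2–2%, and with a single responder it cannot reach 5% for a marker positive in 2 to 19 patients. The mid-p version (Fisher's p less half the probability of the observed table) recovers part of this, with size about 0.8–3.9%. It allows conditional error up to 10%, however, and still gives 0.045 in the three-responder example. Whichever version is chosen should be named before the marker data are analysed.

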Overall, data regarding the long-term outcome of patients with SFT is limited. The estimated incidence is <0.1/100,000/year and SFT is a ubiquitous sarcoma being able to arise from almost all anatomic sites. The natural history of SFT is characterized by a high cure rate after complete surgery, but with a 10-15% risk of metastasis. Metastatic disease is associated with a shortened survival, with lung, bones, and liver being common sites. On the other hand, the percentage of locally advanced disease could be as high as 40% of cases.

Adjuvant radiotherapy has been used to prevent recurrences, but its efficacy still remains to be better studied. Finally, the efficacy of chemotherapy in unresectable and/or metastatic setting is not well established in the current literature. In a retrospective analysis of 36 HPC patients treated at MD Anderson Cancer Center (MDACC), 10 were treated with either neoadjuvant or adjuvant anthracycline therapy. 1/10 experienced major radiographic response (reduction in tumor size > 50%), but chemotherapy did not seem to prolong survival in that group². The Istituto Nazionale dei Tumori reviewed retrospectively the long term outcome of 65 patients operated between 1990-2008. The overall incidence of metastases was 17% (lung was the commonest site). The 5-year post-metastasis overall survival was 45%³. Conventional chemotherapy with doxorubicin or ifosfamide achieved just some stable disease with modest duration.

The rich vascular characteristics of SFT have been long recognized. IHC expression of VEGF has been noted both in SFT tumor cells as well as in endothelium, with VEGFR1 and VEGFR2 overexpressed in endothelium only, suggesting that both autocrine and paracrine activation of the VEGF–VEGFR pathway may exist in SFT biology. Data regarding the molecular pathogenesis of SFT overall, however, are quite limited.

Three pathologic variants have been proposed for SFT: (1) Typical SFT (usually with favorable outcome), (2) Malignant SFT (characterized by higher mitotic index of more than 4 mitosis x 10 HPF; necrosis and pleomorphism) and (3) Dedifferentiated SFT (component of high grade NOS sarcoma).

Due to suspected differences in the outcome between these pathologic variants of SFT, and in order to study these variants deeper, the cohort has been divided into two subgroups: Typical SFT (1-a) (which usually has a more favorable outcome) and malignant/dedifferentiated SFT (1-b) (more aggressive and less responsive).

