Extraskeletal myxoid chondrosarcoma (EMC) is a rare malignant neoplasm characterized by multinodular growth of primitive chondroid cells in an abundant myxoid matrix. It is considered highly resistant to conventional radiation and chemotherapy and surgical removal is the only option for curative treatment. EMC is distinguished from other sarcomas by its unique histology and a characteristic chromosomal translocation, typically t(9;22)(q22;q12.2), fusing EWSR1 to NR4A3 (genes formerly termed EWS and CHN, TEC, or NOR1, respectively). A small proportion of EMC have a different translocation, t(9;17)(q22;q11.2), which results in a RBP56-NR4A3 fusion gene and neuroendocrine differentiation in some cases. The chromosomal translocations result in fusion gene products responsible for alterations in cellular growth and differentiation¹⁴. Less frequently two different translocations t(9;17)(q22;q11,2) and t(9;15)(q22;q21) have been described also in EMC. Most EMC arise from extremities and limb girdles and typically exhibit a very slow growth. Metastases are reported in at least 50% of cases being soft part and lungs the commonest sites. Patients with metastases can live during long-term, thus almost 60% of metastatic patients live more than 15 years.

Interestingly, a dimensional response has been described in a case report of metastatic EMC treated with sunitinib. The authors postulate an inhibition of autocrine/paracrine VEGFR mechanism instead a direct interaction with the fusion protein derived from specific translocation of EMC¹⁵.

Following the previous knowledge, the GEIS-32 trial plans to explore pazopanib¹⁶ prospectively in locally advanced or metastatic SFT and in a second cohort of EMC patients. This compound could also be more suitable than sunitinib or sorafenib in SFT since pazopanib is a less potent Flt-3 inhibitor being thus less myelosuppressive. Moreover, pazopanib has a more favorable safety profile in comparison with sunitinib or sorafenib, a relevant fact considering the potential long-term use in this indication.

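### The gate for multivariable biomarker models counts patients rather than events, so it admits overall survival and response models with too little information behind each variable

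*Protocol*

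**What the plan says.** Protocol section 12.4 sets the rules for the biomarker analyses. The stated aim is "studying the impact of histology, immunohistochemistry and molecular factors on PFS and OS". A Cox model is to be fitted "by using a stepwise selection to identify the independent predictors of poor outcome". The general level is given as "The statistical significance level will be of 5" per cent. Multivariable analysis goes ahead "if the number of cases available for the study is at least 10-fold the number of variables involved"; if that condition fails, "Otherwise, standard univariate pre and post tests will be used".

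Section 11.3 adds a general condition: "Multivariate methods will be used only if the required assumptions are verified". It also foresees multivariate regression of biomarkers on clinical response, without naming a selection method. In section 12.4 itself, the association with response is tested by chi-squared.

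**The concern.** The ratio of 10 is a familiar convention, but the protocol applies it to the wrong quantity. A patient censored without an event adds little to a Cox partial likelihood, so a cohort with few deaths supports few coefficients however many patients it holds. A logistic model for response is limited in the same way by the smaller of the responder and non-responder groups. In slowly progressing tumours, the gap between patients and deaths is large.

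Stepwise selection adds to the problem. Markers that survive it carry estimates that are too large and p-values that are too small. Both tumours are very rare, so a false predictor would be hard to refute by replication, and section 15.5 commits to publishing the translational results.

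**Working it through.** **Inputs from the protocol**
- Stratum sizes 30, 31 and 21 (section 1; section 11.3).
- Recruitment 36 months and follow-up 18 months (section 1). The calendar dates there, second quarter 2014 to second quarter 2018, leave only 12 months, so both were run.
- SFT survival (section 2.1): "The 5-year post-metastasis overall survival was 45" per cent.
- EMC survival (section 2.1): "almost 60% of metastatic patients live more than 15 years".
- SFT PFS: median 8.87 months in the temozolomide/bevacizumab series (section 2.1). No PFS rate is given for EMC, so EMC PFS was not computed.
- Response rates 0.40 and 0.60 for SFT, 0.05 and 0.20 for EMC (section 11.3).

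**Assumptions.** Exponential survival, uniform accrual, and the background rates above applied to the trial cohorts.

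**Step 1: what the rule admits.** The rule has no derived figure to reproduce. The stratum sizes behind it add up: 30 + 31 + 21 = 82, of which 61 are SFT. One variable per 10 cases gives 6 variables for 61, 3 for 30 and 2 for 21.

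**Step 2: expected events.** With accrual *a* and minimum follow-up *f*, the average event probability is P = 1 − [exp(−λf) − exp(−λ(f + a))] / (λa). For 18 months of follow-up:
- SFT OS: λ = −ln(0.45)/5 = 0.1597 per year; P = 1 − (0.7870 − 0.4874)/0.4791 = 0.375. This gives 22.9 deaths in 61 and 11.2 in 30.
- EMC OS: λ = −ln(0.60)/15 = 0.0341 per year; P = 1 − (0.9502 − 0.8579)/0.1022 = 0.097. This gives 2.0 deaths in 21.
- SFT PFS: λ = ln(2)/8.87 = 0.0781 per month; P = 1 − (0.2450 − 0.0147)/2.813 = 0.918. This gives 56.0 events in 61 and 27.5 in 30.

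The ranges below run from 12 to 18 months of follow-up.

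| Model | Cases | Variables by the rule | Expected events | Events per variable | Variables at 10 events each |
|---|---|---|---|---|---|
| SFT pooled, OS | 61 | 6 | 19.7–22.9 | 3.3–3.8 | 1–2 |
| Stratum 1-a, OS | 30 | 3 | 9.7–11.2 | 3.2–3.7 | 0–1 |
| EMC, OS | 21 | 2 | 1.7–2.0 | 0.9–1.0 | 0 |
| SFT pooled, PFS | 61 | 6 | 53.0–56.0 | 8.8–9.3 | 5 |
| Stratum 1-a, PFS | 30 | 3 | 26.1–27.5 | 8.7–9.2 | 2 |

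**Step 3: response.** At either 0.40 or 0.60, the smaller SFT group is 0.40 × 61 = 24.4 pooled (24.4/6 = 4.1 per variable) or 0.40 × 30 = 12 in stratum 1-a (12/3 = 4). EMC at 0.20 gives 0.20 × 21 = 4.2 responders, or 2.1 per variable.

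**Step 4: false selection.** Forward stepwise Cox models were simulated with no true effect, independent binary markers at 50% prevalence, entry at p < 0.05 and 18 months of follow-up. The chance of selecting at least one marker was:
- SFT OS: 28% with 6 variables (median apparent hazard ratio of the first one selected 2.8, direction ignored), 9% with 2.
- SFT PFS: 26% with 6 variables, 24% with 5.
- Stratum 1-a OS: 15% with 3 variables (hazard ratio 4.6).
- EMC OS: 9% with 2 variables, with estimates that diverge.

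**Step 5: which variables are counted.** If candidates are meant, the 12 cytokines of section 12.2 need 12 × 10 = 120 cases; at most 61 SFT patients exist, so that model is blocked. If retained variables are meant, about 15 candidates (cytokines plus tissue markers) could be screened, and the same simulation gives 54% for OS and 58% for PFS.

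**The case against.** Several points can fairly be made for the protocol, and some stand.

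- **PFS.** A reader might infer that all the survival models will be overfitted. The documents do not support that: SFT PFS events nearly equal cases, and an event rule removes only one variable.
- **Certainty.** A reader might also infer that false predictors are bound to appear. For 2 to 6 null variables the chance is roughly 9% to 28% per model, a raised risk. It passes 50% only if about 15 candidates are screened.
- **Cytokine panel.** Read as counting candidates, the gate already stops a model with all 12 cytokines and falls back to univariate tests. It would still admit 6 variables on about 23 deaths.
- **Response.** Stepwise selection is tied to the Cox models. Section 11.3 foresees multivariate regression for response but names no stepwise step, so none should be read into it.
- **Multiplicity.** Twelve cytokines against three outcomes make 36 tests, and 1 − 0.95^36 = 84% is a tempting figure. It assumes independence and describes univariate testing; it would be the same under an event-based gate.
- **Soft inputs.** The SFT survival figure comes from a surgical series of 65 with 17% metastases, so about 11 patients (65 × 0.17), and section 2.1 expects the SFT variants to differ. Section 7.10 follows patients to death where possible, so later analyses could have more deaths.
- **Assumptions clause.** The condition in section 11.3 is general. It sets no event count and does not repair the gate.

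No primary endpoint, sample size or stopping rule depends on these analyses.

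**Conclusion.** The concern holds for OS and for any multivariable response model. The protocol fixes a threshold in the wrong unit, and applying it as written would allow about 3 to 4 deaths per variable in SFT, about 1 in EMC, about 4 per variable in the smaller response group for SFT, and about 2 for EMC. Such models can be overfitted, and stepwise selection makes spurious predictors more likely. For SFT PFS the unit error is nearly harmless; the remaining risk there comes from the selection procedure.

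The counts rest on the quoted background rates, exponential survival and the planned follow-up, and should be read as orders of magnitude. Using 5% as the stepwise threshold is an inference from the general level. That events are the relevant unit does not depend on these assumptions. The ambiguity between candidate and retained variables is a separate drafting gap and decides how much screening the gate permits.

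**What to change.** Keep the factor of 10 and change what it multiplies. Suggested wording for section 12.4:

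*Multivariable models are fitted only with at least 10 events (deaths for OS; progressions or deaths for PFS; the smaller of responders and non-responders for response) per candidate variable, counted separately for each endpoint and analysed cohort. Candidate variables are counted before any selection. Candidates are pre-specified and no stepwise selection is used. Results are reported as exploratory.*

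The change of unit alone is not enough: for SFT PFS it lowers the simulated false-selection rate only from 26% to 24%, which is why stepwise selection should go as well. Penalised estimation and multiplicity adjustment across the cytokine panel are reasonable options but can be left to the SAP.

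The cost is wording only. Some multivariable models, notably EMC OS, will not be run.
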